11.4.2 SECONDARY EFFECTIVENESS ENDPOINT

The number and percent of eyes achieving the secondary effectiveness endpoint will be calculated. The binomial distribution will be used to derive the exact 95% confidence interval of the percent and to perform the statistical hypotheses for the secondary effectiveness endpoint described in Section 11.1.2. It should be noted that, for eyes with secondary surgical interventions (SSI) to control IOP or with SSI that can affect the

IOP before 12 months, the non-responder (i.e. do not achieve the secondary effectiveness endpoint) will be assumed for the missing 12-month response.

For the analyses based on the mITT population, the IOP and number of IOP-lowering medications imputation for missing data described in Section 11.4.1 will be used to derive the corresponding response of the secondary effectiveness endpoint.

11.4.3 COVARIATE ANALYSIS

The following variables will be examined for their prognostic value to the primary and secondary effectiveness endpoints using the PP population with the imputation used for the IOP-related SSIs:

- Age group (based on observed quartiles)
- Gender (male and female)
- Race (White and non-White)
- Ethnicity
- Baseline IOP group (based on observed quartiles)
- Screening Number of IOP-lowering medications (1, 2, 3 and 4)
- Study site

For the primary effectiveness endpoints, one-way ANOVA with one of the factors listed above will be used to check the possible covariate effects. For the secondary effectiveness endpoint, Fisher's test will be performed. A p-value of 0.15 will be used for evaluating the possible covariate effects.

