11 STATISTICAL CONSIDERATIONS

11.1 HYPOTHESES AND SAMPLE SIZE CALCULATION

11.1.1 SAMPLE SIZE FOR THE PRIMARY EFFECTIVENESS ENDPOINTS

First Primary Effectiveness Endpoint

The first primary effectiveness endpoint is the reduction in the unmedicated diurnal IOP from baseline to 12 months postoperatively. The study objective is to show that the mean unmedicated diurnal IOP reduction of the study treatment (i.e. ab-interno transluminal viscoelastic delivery and trabeculotomy performed with OMNI system performed after uneventful cataract extraction) is superior to that of the cataract extraction alone. Based on recent approved MIGS studies, the mean \pm SD unmedicated diurnal IOP reduction at 12 months for the cataract extraction alone is 6.7 mmHg \pm 3.6 mmHg (N = 118) for Glaukos P170043 and 6.3 mmHg \pm 4.0 mmHg (N = 187) for Ivantis P160024. Therefore, the mean \pm SD unmedicated diurnal IOP reduction at 12 months for the cataract extraction alone is estimated as 6.5 mmHg \pm 3.8 mmHg.

The corresponding statistical hypotheses are as follows:

$H_0: \mu_{OMNI} \leq 6.5$ mmHg and $H_a: \mu_{OMNI} > 6.5$ mmHg, where μ_{OMNI} is the mean unmedicated diurnal IOP reduction at 12 months for the OMNI Surgical System in combination with Cataract Extraction.

Based on a one-sample t-test with a one-sided significance level of 0.025 (or two-sided 0.05), a sample size of 116 eyes at 12 months provides a statistical power of 80% at a true μ_{OMNI} of 7.5 mmHg.

Second Primary Effectiveness Endpoint

The second primary effectiveness endpoint is the reduction in the number of IOP-lowering medications from screening to 12 months (before medications washed out if applicable) postoperatively.

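### Section 11.4.3 tests age, baseline IOP and screening drug count only as unordered groups; for age this costs about 10–20 points of power if the effect is roughly linear and modest (r about 0.10–0.30)

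*Combined protocol and SAP*

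**What the plan says.** Section 11.4.3 of the combined protocol and SAP lists seven variables to be examined for association with the primary and secondary endpoints, "using the PP population with the imputation used for the IOP-related SSIs". Three of them are numeric or ordered:

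- age: "Age group (based on observed quartiles";
- baseline pressure: "Baseline IOP group (based on observed quartiles";
- drug count: "Screening Number of IOP-lowering medications (1, 2, 3 and 4".

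For the primary endpoints, "one-way ANOVA with one of the factors listed above will be used to check the possible covariate effects". For the others, "For the secondary effectiveness endpoint, Fisher's test will be performed". The threshold is lenient: "A p-value of 0.15 will be used for evaluating the possible covariate effects".

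The section names no trend test, slope or model on the recorded value. It gives no reason for the quartiles and no power or effect size for this analysis.

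**The concern.** Age and baseline diurnal IOP are collected as numbers (the latter as the mean of three timed readings, Appendix A, Section 20.5), and the drug count is ordered. The planned tests discard information in two ways. Cutting at quartiles ignores variation within each quarter. Treating four ordered groups as nominal spreads the test over 3 degrees of freedom, so a steady rise or fall across the groups gets no credit for its direction.

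Two things are at stake, both modest. A graded association that the data could show is more likely to be missed, which works against the sensitivity that a 0.15 threshold seems meant to give. And because the cut points depend on the sample, a flagged effect cannot be stated per year of age or per mmHg.

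**Working it through.** **Inputs from the plan.** The threshold of 0.15, the quartile grouping and the two tests come from Section 11.4.3. The evaluable number comes from Section 11.1.1: "a sample size of 116 eyes at 12 months provides a statistical power of 80% at a true" mean IOP reduction of 7.5 mmHg, against a null of 6.5 mmHg with SD 3.8. The planning responder rates 0.85 and 0.70 come from Section 11.1.2.

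**Assumptions, not in the plan.** Covariate distribution, shape of effect and effect size. Correlations (r) and odds ratios are therefore shown over a range.

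**The plan's own figure.** Normal formula: (1.960 + 0.842)² × 3.8² / 1.0² = 113.3, so 114. The exact one-sample t calculation gives 116 eyes with power 80.3%. The stated 116 is reproduced.

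**Continuous endpoint, linear effect, normal covariate.** Power comes from the noncentral F distribution with λ = N·ρ²/(1 − ρ²), where ρ² is the share of outcome variance that the test can see.

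- Quartile means of a standard normal are ±1.271 and ±0.325, so quartiles keep ½(1.271² + 0.325²) = 0.861 of the covariate's variance.
- Recorded value at r = 0.20: λ = 116 × 0.04/0.96 = 4.83, 1 df, critical F 2.10, power 77%.
- Quartile ANOVA at r = 0.20: ρ² = 0.861 × 0.04 = 0.0344, λ = 116 × 0.0344/0.9656 = 4.14, 3 df, critical F 1.81, power 57%.
- A 1-df score 1–4 on the same quartiles gives 72%. So about 15 of the 20 points come from ignoring the order and about 5 from the cutting.

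Simulation (20,000 runs per setting, N = 116, p<0.15) agrees:

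| r | Quartile ANOVA | Recorded value | Loss (points) |
|---|---|---|---|
| 0 (null) | 15% | 15% | – |
| 0.05 | 18% | 21% | 3 |
| 0.10 | 26% | 36% | 10 |
| 0.15 | 40% | 57% | 17 |
| 0.20 | 57% | 77% | 20 |
| 0.25 | 74% | 90% | 16 |
| 0.30 | 87% | 97% | 10 |
| 0.35 | 95% | 99% | 4 |
| 0.40 | 99% | 100% | 1 |
| 0.50 | 100% | 100% | 0 |

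Both tests hold their level, so the difference does not come from a higher error rate. The largest loss is 17 points for a uniform covariate and 23 for a skewed one. N = 130 gives similar results.

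**Binary endpoint** (3,000 runs, N = 116, exact 4×2 Fisher test against a 1-df logistic likelihood-ratio test; losses are from unrounded powers):

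| Odds ratio per SD | Fisher, 85% responders | Logistic, 85% responders | Loss at 85% | Loss at 70% |
|---|---|---|---|---|
| 1.2 | 18% | 25% | 7 | 10 |
| 1.35 | 27% | 39% | 13 | 17 |
| 1.5 | 36% | 54% | 18 | 21 |
| 1.75 | 53% | 77% | 24 | 18 |
| 2.0 | 65% | 87% | 21 | 12 |
| 2.5 | 84% | 97% | 13 | 4 |

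**Other shapes, continuous endpoint.**

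- Step at the top quartile, r = 0.20: ANOVA 57% against 56% for the straight line if the step sits at the population quartile, and 63% against 56% if it sits exactly at the observed cut.
- U-shape: ANOVA 34% against 18% at r = 0.20, and 55% against 22% at r = 0.30.

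**Baseline IOP against IOP reduction.** Baseline is part of this outcome, so a larger correlation is plausible. Assume a baseline SD of 2.5–3 mmHg and a slope of 0.5–0.7. With the plan's SD of 3.8, r runs from 0.5 × 2.5/3.8 = 0.33 to 0.7 × 3/3.8 = 0.55. Read against the first table, the loss is about 6 points falling to 0.

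**Drug count.** The four categories are the recorded values, so nothing is lost within groups. If the effect is linear in the count, both tests have the same λ and differ only in degrees of freedom. At r = 0.10 / 0.15 / 0.20 / 0.25, power is 28 / 44 / 63 / 80% on 3 df against 36 / 58 / 77 / 91% on 1 df. The count is also part of the second primary outcome, so these correlations may be too low for that endpoint.

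**The case against.** The strongest reply is that an omnibus test on prespecified quartiles is a conventional screen that assumes no shape. The plan gives no reason to expect a linear effect, the threshold is already lenient, and replacing the test with a straight line would give up sensitivity to non-monotone effects: 33 points for the U-shape at r = 0.30. This stands as an argument for keeping the quartile tests. It does not justify having only them, since for an ordinary graded effect they are clearly the weaker choice and yield no slope.

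A reader might infer that all three covariates lose 10–20 points whatever the effect. The documents do not support that. They give no covariate effect size or shape, baseline IOP is built into the first primary outcome, and the drug count is not cut at all.

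A reader might also infer that, in a single-arm study judged against fixed goals, this analysis is what shows whether patient mix drives the result. That does not follow. A prognostic slope within one arm cannot show it without the covariate distributions of the historical cataract-only groups, which the proposed change would not supply. Section 11.3 separately describes the patient mix for the treated, mITT and PP populations.

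**Conclusion.** The point holds as a cheap improvement to an exploratory analysis. For age, at 116 eyes and p<0.15, the planned tests lose about 10–20 points of power if the effect is roughly linear with r about 0.10–0.30. The size rests on those illustrative correlations and, in the main table, on a normal covariate. Outside that range the loss is small: 3 points at r = 0.05 and 4 or fewer from r = 0.35.

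No test is invalid and no error rate is affected. Section 11.4.3 attaches no action to a flagged covariate, and the hypothesis tests in Sections 11.1, 11.4.1 and 11.4.2 do not use its results.

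**What to change.** In Section 11.4.3:

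- Make the main test for age and baseline IOP a 1-df test on the recorded value, and for the screening drug count a 1-df ordered score. Use linear regression for the primary endpoints and logistic regression for the secondaries, at the same 0.15 threshold.
- Report each slope with its 95% CI (per year, per mmHg, per medication).
- Keep the ANOVA and Fisher results on the quartile and drug-count groups as a stated supportive check for non-monotone patterns. State that the 1-df test decides whether a covariate is flagged, so that taking the better of two tests does not push the false-flag rate above 15%.
- Leave gender, race, ethnicity and site as categorical tests.

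The cost is a few lines of SAP text and code, using data already collected. The small downside is one extra supportive test for each of the three covariates on each endpoint (3 × 4 = 12 in all) in an analysis that supports no formal claim.

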11.4.4 ADDITIONAL EFFECTIVENESS ANALYSES

The analyses will be based on the PP population.

- The IOP, change in IOP, percent change in IOP, number of IOP-lowering medications, and change in number of IOP-lowering medications will be summarized descriptively at each visit along with the 95% confidence intervals based on the t-distribution.
- The outcome of $\geq 20\%$ reduction in IOP with no IOP-lowering medications at each visit will be summarized by count and percent of eyes achieving the outcome.
- The outcome IOP of ≥ 6 mmHg and ≤ 18 mmHg with no IOP-lowering medications at each visit will be summarized by count and percent of eyes achieving the outcomes.
- The distribution of 12-month unmedicated diurnal IOP percent change from baseline will be prepared for the following categories stratified by the number of IOP-lowering medication change from baseline and the IOP-related SSIs:
 - $40\% \leq \text{Change}$ (i.e. increase $\geq 40\%$)
 - $30\% \leq \text{Change} < 40\%$ (i.e. $30\% \leq \text{increase} < 40\%$)

- 20% ≤ Change < 30% (i.e. 20% ≤ increase < 30%)
- 10% ≤ Change < 20% (i.e. 10% ≤ increase < 20%)
- 0% < Change < 10% (i.e. 0% < increase < 10%)
- Change = 0% (i.e. no change)
- -10% < Change < 0% (i.e. 0% < decrease < 10%)
- -20% < Change ≤ -10% (i.e. 10% ≤ decrease < 20%)
- -30% < Change ≤ -20% (i.e. 20% ≤ decrease < 30%)
- -40% < Change ≤ -30% (i.e. 30% ≤ decrease < 40%)
- -50% < Change ≤ -40% (i.e. 40% ≤ decrease < 50%)
- Change ≤ -50% (i.e. decrease ≥ 50%)
- The distribution of 12-month unmedicated diurnal IOP will be prepared for the following categories stratified by the number of IOP-lowering medication change from baseline and the IOP-related SSIs:
 - ≥6 mmHg to ≤ 21 mmHg
 - ≥6 mmHg to ≤ 18 mmHg
 - ≥6 mmHg to ≤ 15 mmHg
 - ≥6 mmHg to ≤ 12 mmHg
- The survival analysis (Kaplan Meier curve) for the time to the first IOP-related SSIs will be performed. The survival analysis will also be performed for the time to first take the systemic IOP-lowering medications

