A record of all ocular hypotensive medications added, discontinued or changed will be documented on the appropriate Case Report Form for each scheduled visit or on a Case Report Form for an Unscheduled Visit, if necessary.

Another potential reason for intervention is hypotony. Intervention should only be considered if the hypotony has caused or is likely to cause sequelae such as a flat chamber. No intervention is indicated when the vision is unchanged from screening, there is no persistent choroidal detachment, the anterior chamber is not flat with lens corneal touch, or the patient is asymptomatic. No intervention should be undertaken for hypotony which is not causing, or threatening to cause, a reduction in vision.

Secondary IOP-Lowering Interventions to Control IOP

If the subject requires another glaucoma procedure to control their IOP, the subject should continue to be followed according to standard of care until the adverse event resolves or 1 month post-re-intervention, whichever is longer. Following this, the subject should be withdrawn from the study.

Subjects who have a secondary IOP-lowering intervention will be considered treatment failures for the purpose of the secondary endpoint analyses. These subjects will be included in the Safety Endpoint analyses through their withdrawal from the study.

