11.2 ANALYSIS POPULATIONS

The intent-to-treat (ITT) analysis population includes all subjects who are enrolled and treated, regardless of whether or not they have a protocol deviation. Due to the eligibility revision in May of 2019 on requiring at least one ocular hypotensive medication, the modified ITT (mITT) population includes all ITT except for the treated eyes that were not on any ocular hypotensive medication at the screening visit. The per-protocol analysis population (PP) is a subset of mITT, which includes all subjects who have taken at least one ocular hypotensive medication at screening and have uneventful cataract extraction followed by ab-interno transluminal viscoelastic delivery and trabeculotomy, 12 month IOP and medication data, and have no clinically significant protocol deviations. It should be noted that the mITT subjects with an uneventful study procedure but with SSIs before the 12-month visit will be included in the PP population even if they do not have the 12-month IOP and medication data. The primary analyses on the primary and secondary endpoint analyses will be carried out on the per-protocol population.

The safety data will be summarized based on the ITT population. The primary and secondary endpoint analyses will also be performed on the mITT population.

The data will be listed separately for the enrolled subjects that are not treated with OMNI and treated subjects that do not have ocular hypotensive medications at the screening.

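### The Kaplan-Meier curves and per-visit summaries use only the PP population, so event-free eyes lost early are deleted rather than censored; this builds a small upward bias into the SSI curve

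*Combined protocol and SAP*

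**What the plan says.** Section 11.4.4 (Additional Effectiveness Analyses) opens with its population: "The analyses will be based on the PP population". Under that heading come the descriptive summaries of IOP and medication count at each visit and two time-to-event analyses. The first is for secondary surgery: "The survival analysis (Kaplan Meier curve) for the time to the first IOP-related SSIs will be performed". The second is for systemic treatment: "The survival analysis will also be performed for the time to first take the systemic IOP-lowering medications". Section 11.4.4 gives no censoring rule.

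Section 11.2 (Analysis Populations) defines PP as a subset of mITT. Besides medication at screening and an uneventful procedure, an eye must have "12 month IOP and medication data, and have no clinically significant protocol deviations". There is one exception: mITT eyes with an uneventful procedure and an SSI before 12 months "will be included in the PP population even if they do not have the 12-month IOP and medication data".

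The wider population is used elsewhere, but not here. Section 11.2 says "The primary and secondary endpoint analyses will also be performed on the mITT population", and Section 11.4 repeats this. Neither extends it to the analyses in 11.4.4. Safety is summarised on ITT (Section 11.5).

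After a further glaucoma procedure, Section 9.9 has the subject followed for a limited period, and then: "Following this, the subject should be withdrawn from the study". Without the exception in 11.2, such eyes would usually have no 12-month data and would drop out of PP.

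**The concern.** Kaplan-Meier exists to use partial follow-up. An eye last seen at 6 months with no SSI should count as at risk for those 6 months and then be censored. Under the PP rule it is deleted, because of something that happens later: it has no 12-month visit. An eye that had an SSI and then left is kept. Membership of the risk set thus depends on the future and, for the SSI curve, on the event itself. Almost no censoring before 12 months remains, and the curve reduces to roughly SSI eyes divided by SSI eyes plus completers.

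The other displays share the selection but not the same mechanism. An eye that took systemic medication and then left without an SSI is lost together with its event. The early-visit summaries leave out eyes that were in fact measured at those visits.

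What is at stake is the accuracy of the reported SSI-free and systemic-medication-free curves and of the visit-by-visit IOP and medication tables. No hypothesis test is involved.

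**Working it through.** **Inputs from the plan.** Section 11.1.1: 116 eyes needed at 12 months, mean reduction 7.5 against 6.5 mmHg, SD 3.8 mmHg, one-sided level 0.025, power 80%, dropout about 10%, about 130 eyes treated. Section 11.1.3 later raises the total to about 145 because some eyes already treated had no medication at screening. About 130 is therefore the working size for mITT.

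**Plan's own figure.** The noncentral-t power for a difference of 1.0, SD 3.8 and n = 116 is 80.3%, and 116 is the smallest n that reaches 80%. Allowing for dropout, 116 / 0.90 = 128.9, or 129, which agrees with the stated figure of about 130. At 10% dropout the PP rule removes about 0.10 × 130 = 13 eyes. The plan gives no figure for the Kaplan-Meier analyses.

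**Assumptions.** The documents give no SSI risk, so the 12-month risk s is assumed. SSI and dropout are independent with constant hazards. PP exclusions for protocol deviations are not modelled.

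**SSI curve, closed form.** With dropout d, let a = −ln(1 − s) and b = −ln(1 − d).

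- Share with an observed SSI: E = a/(a + b) × [1 − (1 − s)(1 − d)]
- Share event-free and complete: F = (1 − s)(1 − d)
- PP estimate at 12 months: E/(E + F)

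For s = 0.05 and d = 0.10: a = 0.0513, b = 0.1054, E = 0.327 × 0.145 = 0.0475, F = 0.855. PP estimate = 0.0475/0.9025 = 5.26%, an excess of 0.26 points.

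For s = 0.05 and d = 0.20: a = 0.0513, b = 0.2231, E = 0.187 × 0.240 = 0.0449, F = 0.760. PP estimate = 0.0449/0.8049 = 5.57%, an excess of 0.57 points.

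Excess over a range of assumed risks:

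| Dropout | s = 1% | s = 5% | s = 10% | s = 20% |
|---|---|---|---|---|
| 5% | 0.03 | 0.12 | 0.24 | 0.43 |
| 10% | 0.05 | 0.26 | 0.50 | 0.90 |
| 20% | 0.12 | 0.57 | 1.09 | 1.95 |

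(Percentage points.) Across this range the relative excess is 4.5% to 5.4% at 10% dropout and about 10% to 12% at 20%. A simulation of 400,000 eyes at 10% dropout agrees: true risk 4.98%, mITT curve with censoring 4.99%, PP curve 5.25%.

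**Systemic-medication curve, same simulation.** The assumed 12-month risk is 5%, and SSI eyes are censored at SSI. The multipliers on the dropout hazard after systemic medication are assumptions.

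| Dropout after systemic medication | True | mITT | PP |
|---|---|---|---|
| Unchanged | 5.04% | 5.06% | 5.05% |
| 5 times the hazard | 4.94% | 4.95% | 4.10% |
| 10 times the hazard | 5.01% | 4.99% | 3.29% |

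With independent dropout there is no visible bias. With informative dropout PP reads low, while mITT stays on target.

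**Per-visit summaries.** With 10% of eyes removed, a mean shifts by about 0.10 × (mean of eyes kept − mean of eyes removed). An assumed gap of 1 to 3 mmHg gives 0.1 to 0.3 mmHg. If dropout is unrelated to IOP the shift is essentially nil, apart from a slight over-weighting of SSI eyes.

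**The case against.** The strongest reply is that this matters little. At the planned dropout and an assumed 5% risk, the excess of 0.26 points is about one-third of an eye (0.0026 × 130 = 0.34). The sampling standard error is √(0.05 × 0.95/130) = 1.9 points, so the bias is about one-seventh of it. It also runs against the device, so it cannot support a favourable claim. The analyses carry no test, and using one population for the primary analysis and its supporting displays is a defensible choice. All of this stands, and it sets the priority of the point.

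It can also be said that the events are reported elsewhere. Section 10.2 lists secondary surgery for IOP, and systemic medication for raised IOP at or after the 1-month visit, as adverse events. Section 11.5.1 counts them on ITT. This stands in part. Those are crude percentages, not time-to-event estimates. The listed systemic-medication event also does not cover use before the 1-month visit, although a prior case series in Section 5 describes pressure spikes 1–2 days after surgery treated with systemic drugs.

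A reader might infer that every output in 11.4.4 is biased. The documents do not support that. The exception in 11.2 makes bias structural for the SSI curve only; for the rest it needs dropout related to outcome, on which the documents give no information. Nor does PP contain only completers: SSI eyes that were withdrawn remain in it, including any that had used systemic medication. Finally, nothing here undermines the primary result, since the primary and secondary endpoints are also analysed on mITT.

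**Conclusion.** The point holds as a minor flaw in analysis population. Followed as written, the plan produces an SSI curve that is too high even under independent dropout: about 5.3% instead of 5.0% at the planned 10% dropout, and about 5.6% at 20%. The direction follows from the PP definition. The size rests on an assumed SSI risk and constant, independent hazards, and it ignores PP exclusions for protocol deviations.

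For the systemic-medication curve and the per-visit summaries, bias is conditional on dropout being related to outcome. If systemic-medication users left more often, that curve would read low. What is certain for these displays is only that valid early observations are discarded. The primary conclusion does not depend on any of them.

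**What to change.** In Section 11.4.4:

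- Run both Kaplan-Meier curves on mITT, censoring eyes without the event at last contact or study exit. ITT versions can be added.
- Base the per-visit summaries on all mITT eyes observed at each visit. mITT is preferable to ITT here because ITT would bring back the eyes with no medication at screening, which Section 11.2 deliberately sets apart.
- Keep the PP versions as supportive displays.

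This is a short text change and needs no new data. The cost is a little extra analysis, and these displays would no longer use exactly the same population as the PP primary analysis.
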